## APPENDIX V- MAXIMUM BLOOD WITHDRAWAL VOLUMES

Table 4 IRB Maximum Allowable Total Blood Draw Volumes (Clinical + Research)

Body Wt (Kg)	Body Wt (lbs)	Total blood volume (mL)	Maximum allowable volume (mL) in one blood draw (= 2.5% of total blood volume)	Total volume (clinical + research) maximum volume (mL) drawn in a 30- day period	Minimum Hgb required at time of blood draw	Minimum Hgb required at time of blood draw if subject has respiratory/CV compromise
1	2.2	100	2.5	5	7.0	9.0 -10.0
2	4.4	200	5	10	7.0	9.0-10.0
3	6.3	240	6	12	7.0	9.0-10.0
4	8.8	320	8	16	7.0	9.0-10.0
5	11	400	10	20	7.0	9.0-10.0
6	13.2	480	12	24	7.0	9.0-10.0
7	15.4	560	14	28	7.0	9.0-10.0
8	17.6	640	16	32	7.0	9.0-10.0
9	19.8	720	18	36	7.0	9.0-10.0
10	22	800	20	40	7.0	9.0-10.0
11-15	24-33	880-1200	22-30	44-60	7.0	9.0-10.0
16-20	35-44	1280-1600	32-40	64-80	7.0	9.0-10.0
21-25	46-55	1680-2000	42-50	64-100	7.0	9.0-10.0
26-30	57-66	2080-2400	52-60	104-120	7.0	9.0-10.0
31-35	68-77	2480-2800	62-70	124-140	7.0	9.0-10.0
36-40	79-88	2880-3200	72-80	144-160	7.0	9.0-10.0
41-45	90-99	3280-3600	82-90	164-180	7.0	9.0-10.0
46-50	101-110	3680-4000	92-100	184-200	7.0	9.0-10.0
51-55	112-121	4080-4400	102-110	204-220	7.0	9.0-10.0
56-60	123-132	4480-4800	112-120	224-240	7.0	9.0-10.0
61-65	134-143	4880-5200	122-130	244-260	7.0	9.0-10.0
68-70	145-154	5280-5600	132-140	264-280	7.0	9.0-10.0
71-75	156-185	5680-6000	142-150	284-300	7.0	9.0-10.0
76-80	167-176	6080-6400	152-160	304-360	7.0	9.0-10.0
81-85	178-187	6480-6800	162-170	324-340	7.0	9.0-10.0
86-90	189-198	6880-7200	172-180	344-360	7.0	9.0-10.0
91-95	200-209	7280-7600	182-190	364-380	7.0	9.0-10.0
96-100	211-220	7680-8000	192-200	384-400	7.0	9.0-10.0

Source: Tables used by the Committee on Clinical Investigations, Children's Hospital in Los Angeles, CA; Baylor College of Medicine, Dallas, TX; and Cincinnati Children's Hospital Institutional Review Board, OH

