## 7. STUDY DESIGN AND PLAN

This will be a Phase III, multicenter, open-label, non-randomized study. Up to 50 subjects will be enrolled to ensure 30 evaluable subjects. At least 18 subjects will be adults (aged 16-75 years) and 12 will be children split between the age groups 2 to 5 years (i.e. not reached their 6th birthday), 6 to 11 years (i.e. not reached their 12th birthday) and 12 to 15 years (i.e. not reached their 16th birthday), with a minimum of 4 in each age group.

All children who receive at least one infusion of Subgam-VF will be included in the safety analysis. Due to the potential for early withdrawals, PK data may not be available on all 12 children and there may be fewer than 12 evaluable children in the PK analysis. The total number of subjects (adults plus children) evaluable for PK analysis will be at least 30.

Subjects will receive 26 infusions (weeks) of Subgam-VF at a weekly dose equivalent to 1.37 of their IGIV dose (expressed as mg/kg/week). If the subject was already receiving a weekly SCIG IgG there will be no dose adjustment. Pharmacokinetics and safety of Subgam-VF will be assessed.

All subjects will undergo a pharmacokinetic (PK) profile after the 21st infusion of Subgam-VF (see PK Assessment Schedule, Table 3). Where an appropriately qualified member of the study team is available, arrangements will be made to collect the PK samples from Steady State Day 1 (24 hours post-infusion) onwards at the subject's home to reduce the number of visits to the sites. Alternatively a Home Health Agency may be utilized to take the PK samples outside of the investigational site. The subject would be required to sign an extra IRB/EC approved consent form to permit the site to share the subject's details with the agency in order for them to collect the sample.

In the case of younger children it is important not to exceed the maximum blood withdrawal volumes stated in Appendix V. Therefore smaller volumes of blood will be taken. See the Laboratory Manual for details.

- Following a screening period, eligible subjects will commence weekly Subgam-VF treatment; this is a 16% subcutaneous IgG product.
- Subjects will receive Subgam-VF for 26 weeks during which time safety will be assessed

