#### 7.3. Pharmacokinetics

All subjects will participate in the pharmacokinetic (PK) segment of the study (if blood withdrawal volumes allow), see Appendix IV, Table 3. In the case of younger subjects, pediatric blood volumes will need to be taken to ensure the maximum blood withdrawal volumes specified in Appendix V are adhered to (see Laboratory Manual for more details).

- In exceptional circumstances, and with prior Sponsor approval, if one of the following PK samples if lost, unevaluable, or not taken it may be taken at the same timepoint during the week following the PK assessment, as long as the same dose in mg/kg has been given:
  - $\circ$  1 day (24 hours  $\pm$  2 hours)
  - $\circ$  2 days (48 hours  $\pm$  4 hours)
  - $\circ$  3 days (72 hours  $\pm$  6 hours)
  - $\circ$  5 days (120 hours  $\pm$  8 hours).

Where possible, arrangements to collect PK samples at the subject's home, from Steady State Day 1 onwards, by a suitably qualified member of the study may be made.

IMPORTANT: If the infusion just prior to PK sampling has to be rescheduled, then the PK sampling should be postponed to ensure that the PK samples are collected seven days after the last Subgam-VF infusion and the sampling times in Table 3 are adhered to.

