# 7.4.4. Reserve Samples

Reserve plasma and serum samples will be collected at all relevant time points, for reanalysis if needed, e.g. if an original sample is spoiled or if results are discrepant. Where necessary an additional blood sample will be collected; at other time points plasma or serum aliquots will be split so that a reserve plasma or serum sample can be retained at site. See Appendix IV and Laboratory Manual.

Reserve samples should be sent to the central laboratory within one month of collection where they will be stored at -70°C for the duration of the study. Reserve samples may be kept until the licence for Subgam-VF is granted by the relevant regulatory authorities and will be used, if required, for repeat assays at the request of a regulatory agency. For full details, please see separate Laboratory Manual.

Table 4 (Appendix V) displays the suggested maximum blood withdrawal for children. If the volume of blood withdrawn within 30 days is expected to exceed that specified on Table 4, then the Sponsor/Contract Research Organization (CRO) should be contacted to discuss order of priority for blood sampling. In these cases it will likely be the reserve samples that will not be taken so as to not exceed the maximum blood volumes allowed. The deviation must be documented appropriately on the eCRF.

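### Two 30-day blood-volume limits in Appendix V, Table 4 break the pattern of the other 44 endpoints, and the 21-25 kg entry could needlessly restrict sampling in a small child

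*Protocol*

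**What the plan says.** Protocol Appendix V, Table 4 gives, for each weight or weight band, total blood volume, a single-draw maximum and a 30-day maximum. The column header defines the single-draw maximum as 2.5% of total blood volume. It gives no formula for the 30-day maximum.

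Three rows are at issue; columns run kg, lb, blood volume, single draw, 30-day:

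- "21-25 46-55 1680-2000 42-50 64-100"
- "76-80 167-176 6080-6400 152-160 304-360"
- "68-70 145-154 5280-5600", which follows directly after the 61-65 kg row.

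The body of the protocol makes the table an operating threshold:

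- Section 7: "In the case of younger children it is important not to exceed the maximum blood withdrawal volumes stated in Appendix V".
- Section 7.3, for younger subjects: "pediatric blood volumes will need to be taken to ensure the maximum blood withdrawal volumes specified in Appendix V are adhered to". Taking part in the PK segment is itself subject to blood volumes allowing it.
- Section 7.4.4 is softer, "Table 4 (Appendix V) displays the suggested maximum blood withdrawal for children", but attaches a procedure. It begins "If the volume of blood withdrawn within 30 days is expected to exceed that specified on Table 4"; the Sponsor or CRO is then contacted about sampling priority, reserve samples are the likely ones to be given up, and the deviation is recorded in the eCRF.

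**The concern.** A limit scaled to blood volume should not fall as weight rises. With each range read from its lightest to its heaviest weight, the 30-day limit falls twice: between 20 and 21 kg, and between 80 and 81 kg. Nothing elsewhere in the protocol explains either step.

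The first step is the one that could touch this trial. Section 7.4.4 acts on the 30-day column, and that is the column with the odd entries. A site with a 21 kg child cannot tell whether 64 mL is intended, since a lighter child is allowed 80 mL. Twelve children are planned, with at least four in each age group, so even one avoidable restriction is worth preventing when the correction is cheap.

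**Working it through.** **Inputs.** All 28 rows of Table 4: 10 single weights (1 to 10 kg) and 18 bands (11-15 to 96-100 kg), giving 10 + 2 × 18 = 46 endpoints.

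**Step 1: the table's stated rule.** Single draw = 0.025 × blood volume. This reproduces all 46 single-draw endpoints. For example, 0.025 × 1680 = 42 mL at 21 kg and 0.025 × 6400 = 160 mL at 80 kg. The blood-volume and single-draw columns therefore agree with each other throughout.

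**Step 2: the implied 30-day rule.** 30-day limit = 2 × single draw = 0.05 × blood volume. This rule is inferred, not written. It reproduces 44 of 46 endpoints. The exceptions, with their neighbours:

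| Weight | Blood volume (mL) | Single draw (mL) | 30-day, stated (mL) | Stated / blood volume | 2 × single draw (mL) |
|---|---|---|---|---|---|
| 20 kg | 1600 | 40 | 80 | 5.0% | 80 |
| **21 kg** | 1680 | 42 | **64** | 3.8% | 84 |
| 25 kg | 2000 | 50 | 100 | 5.0% | 100 |
| 76 kg | 6080 | 152 | 304 | 5.0% | 304 |
| **80 kg** | 6400 | 160 | **360** | 5.6% | 320 |
| 81 kg | 6480 | 162 | 324 | 5.0% | 324 |
| 85 kg | 6800 | 170 | 340 | 5.0% | 340 |

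Departures from the pattern:
- 21 kg: 84 − 64 = 20 mL too low; 20/84 = 24%.
- 80 kg: 360 − 320 = 40 mL too high; 40/320 = 12.5%.

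**Step 3: a check that does not need the 5% rule.** The stated limit falls from 80 to 64 mL between 20 and 21 kg, and from 360 to 324 mL between 80 and 81 kg. Even 85 kg (340 mL) is below 80 kg. With 84 and 320 in place of the two entries, the column no longer falls at any step. These two values are what the table's own pattern implies; they are not proposed limits.

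**Step 4: the 68-70 kg label.** From 3 kg up, blood volume is 80 mL/kg at every endpoint except this one: 5280/68 = 77.6 mL/kg. Working back, 5280/80 = 66 kg, and 145 lb is also about 66 kg. The row's other columns start at 66 kg while its kg label starts at 68. This is the only gap between kg bands.

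**Step 5: when the 21 kg entry would bind.** It changes what a site does only if the planned 30-day volume V at 21 kg satisfies 64 < V ≤ 84 mL. At or below 64 mL neither figure is exceeded; above 84 mL both are. The documents give no per-visit volumes, so V is unknown.

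**The case against.** The strongest reply is that this may not be an error in the plan at all. The text was read from PDF by a program, and each anomaly is one digit away from the pattern (64 for 84, 360 for 320, 68 for 66). The table is also credited to outside hospital and IRB tables, and its header states no 5% rule. All of this stands: the digits must be confirmed first, and the departure is from a pattern, not from a written rule. The fall in the limit with rising weight remains on the text as it reads.

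Four stronger readings are tempting, and the documents do not support them:

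- *Hard limits for every subject.* Sections 7 and 7.3 address younger children and younger subjects, and section 7.4.4 calls the table a suggestion for children. The 80 kg entry therefore has little bearing on this trial, and a real loss of safety margin is not shown.
- *No limit at 66-67 kg.* Only the kg label has a gap. 66-67 kg is about 145.5-147.7 lb, which lies within that row's pounds range.
- *Small children will lose samples.* That needs V in the window of Step 5, which cannot be established without the Laboratory Manual. The 21 kg entry also errs towards caution for the child, and the 25 kg end of the row fits the pattern.
- *The primary analysis is affected.* Section 7.4.4 points to reserve samples as the likely loss. Sections 7 and 7.3 already call for smaller pediatric volumes, and section 12 foresees lighter PK sampling in children. No effect on AUC, the PK population or power follows.

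**Conclusion.** The inconsistency holds on the text as it reads, and its severity is minor. Only the 21-25 kg row could plausibly affect conduct, and its effect is conditional: a possible unneeded contact with the Sponsor or CRO, and possible loss of reserve samples, in a child near 21 kg. The 76-80 kg entry and the 68-70 kg label are corrections to make at the same time.

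This rests on three assumptions: the digits match the original PDF; each range runs from the lightest to the heaviest weight in its band; and the 5% pattern, inferred from the other 44 endpoints, was intended throughout the column.

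**What to change.** 1. Confirm in the original PDF the 30-day entries for 21-25 kg and 76-80 kg and the kg label 68-70.
2. If they read as here, check them against the source tables credited under Table 4 and reconcile them with the adjacent single-draw and blood-volume columns. The correct limits are for the sponsor to establish; none is proposed here.
3. Reissue Table 4. Two slips in the pounds column can be corrected in the same pass, and neither changes a 30-day limit: 3 kg is shown as 6.3 lb (about 6.6), and 71-75 kg as 156-185 lb (75 kg is about 165 lb, and the range overlaps the next band).

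The cost is one clarification letter covering one appendix table. No change to the design, sample size or analysis is needed.

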eCRF Electronic Case Report Form FDA U.S. Food & Drug Administration

kg Kilogram

K_{elim} Elimination Rate Constant

ICH International Conference on Harmonization of Technical Requirements for

Registration of Pharmaceuticals for Human Use

IgA Immunoglobulin A
IgG Immunoglobulin G

IGIV Immunoglobulin Intravenous

IgM Immunoglobulin M

IMP Investigational Medicinal Product

ITT Intent-to-treat

LLQ Lower Limit of Quantification

MedDRA Medical Dictionary for Regulatory Activities

mg Milligram mL Milliliter

MRT Mean Residence Time
PID Primary Immunodeficiency

PK Pharmacokinetic
PT Preferred Term
SAE Serious Adverse Event
SAP Statistical Analysis Plan
SD Standard Deviation

SI Units International System of Units

SOC System Organ Class

SOP Standard Operating Procedure

SUSAR Suspected Unexpected Serious Adverse Reaction

 $t_{\text{max}} \hspace{1.5cm} \text{Time at which C_{max} first occurs}$

 $t_{1/2}$ Half-life

TEAE Treatment Emergent Adverse Event

Vd Volume of Distribution

WHO-DD World Health Organization-Drug Dictionary

1. Revision History

Version	Date	Document Owner	Revision Summary
1.0	12 January 2017	[name]	Final

2. RELEVANT DOCUMENTS AND STANDARDS

2.1 Protocol, Amendments, CRF and SAP Version

Protocol Version 5.0 (28 April 2016) Annotated CRF Version 1.0 (08 September 2015)

2.2 Applicable Standards

ICH Guidance on Statistical Principles for Clinical Trials (ICH E9)

ICH Guidance on the Structure and Content of Clinical Study Reports (ICH E3)

ICH Guidance for Good Clinical Practice (ICH E6)

3. PURPOSE OF THE ANALYSIS

The purpose of this Statistical Analysis Plan (SAP) is to outline the planned analyses to support the completion of the Clinical Study Report (CSR) for protocol SCIG03. The planned analyses identified in this SAP will be included in regulatory submissions and/or future manuscripts. Exploratory analyses not identified or defined in this SAP may be performed to support the clinical development program. Any post-hoc or unplanned analyses performed and not identified in this SAP will be documented in the respective CSR.

PK analyses are not included in this SAP but documented separately in PK Analysis Plan.

4. STUDY OBJECTIVES

4.1 Primary Objective

 To determine the PK profile of Subgam-VF and compare the AUC(0-τ) with historical AUC data (all standardized to one week at steady state) from Gammaplex 5% IGIV PID studies (GMX01 and GMX04).

4.2 Secondary Objectives

- To assess the safety of Subgam-VF, including the incidence of adverse events and site infusion reactions in subjects with PID.
- To refine the dose adjustment coefficient for Subgam-VF.

4.3 Exploratory Objective

To explore PK modelling for alternative dosing schedules

5. STUDY METHODS

5.1 Overall Study Design

This will be a Phase III, multicenter, open-label, non-randomized study. Up to 50 subjects will be enrolled to ensure 30 evaluable subjects. At least 18 subjects will be adults* (aged 16-75 years) and 12 will be children split between the age groups 2 to 5 years (i.e. not reached their 6th birthday), 6 to 11 years (i.e. not reached their 12th birthday) and 12 to 15 years (i.e. not reached their 16th birthday).

*The definition of an adult as ≥ 16 years is as per the FDA guidance for PK studies. Note this does not affect the requirements for consent/assent, for which each site should follow their IRB guidelines.

Subjects will receive 26 infusions (weeks) of Subgam-VF at a weekly dose equivalent to 1.37 of their IGIV dose (expressed as mg/kg/week). If the subject was already receiving a weekly SCIG IgG there will be no dose adjustment. Pharmacokinetics and safety of Subgam-VF will be assessed.

The schedule of assessments is given in Table 1.

All subjects will undergo a pharmacokinetic (PK) profile after the 21st infusion of Subgam-VF. Pharmacokinetic Assessment Schedule for Subgam-VF (Week 21 to Week 22) is given as outlined in Table 2.

Table 1 Schedule of Assessments

Assessment																		
(Wk)	Screen	1 ^a	2	3 to 4	5	6 to 8	9	10 to 12	13	14 to 16	17	18 to 20	21	22	23 to 25	26	27 FU ^b	30 Telephone FU°
Clinic Visit No.	1	2	3		4		5		6		7		8	9		10	11	
Informed Consent	Х																	
Inclusion /Exclusion Criteria / Eligibility	Х	Х																
Medical History	Х																	
Physical Examination	X	Х							Х								Χ	
Weight	X	Х	Х		Х		Х		Х		Х		Х	Х		Х	Χ	
Chest X-ray – if not available in previous 12 months		Х																
Vital signs ^d	Х	Х	Х		Х		Х		Х		Χ		Χ	Х		Х	Χ	
Infusion with Subgam-VF		Х	Х	Х	Х	Х	Х	Х	Х	Х	Х	Х	Х	Х	Х	Х		
Infusion Site Inspection for reactions		Х	Х	Х	Х	Х	Х	Х	Х	Х	Х	Х	Х	Х	Х	Х		
Concomitant medications	Х	Х	Х	Х	Х	Х	Х	Х	Х	Х	Х	Х	Х	Х	Х	Х	Х	Х
Adverse event reportinge	Х	Х	Х	Х	Х	Х	Х	Х	Х	Х	Х	Х	Х	Х	Х	Х	Х	Х
TEE examination ^f	X																Χ	
Hematology	X	Х	Χ		Χ		Χ				Χ						Χ	
Biochemistry	X	Х	Х		Χ		Χ				Χ						Χ	
Urinalysis	Χ	Х									Χ						Χ	
HCG urine pregnancy test	X																	
lgG trough levels	X	Х	Х		Χ		Х		Χ		Χ		Χ	Х		Х	Х	
IgA, IgM ^g	Х																	
lgG subclasses	X																Χ	
Specific anti-bodies h	X																Χ	
Virology i	X																Х	
Parvovirus B19 ^j		Х	Х														Х	
Direct Coombs' Test k		Х	Χ						Χ								Х	

Assessment																		
(Wk)	Screen	1 ^a	2	3 to 4	5	6 to 8	9	10 to 12	13	14 to 16	17	18 to 20	21	22	23 to 25	26	27 FU ^b	30 Telephone FU ^c
Clinic Visit No.	1	2	3		4		5		6		7		8	9		10	11	
Haptoglobin, plasma free hemoglobin, urine hemosiderin		Х	Х						Х								Х	
PK assessment ^m													Χ	Χ				
Study Diary issue	Χ	Χ	Х	Χ	Х	Χ	Х	Χ	Χ	Χ	Χ	Χ	Χ	Χ	Χ	Х		
Reserve sample	Χ	Χ	Χ		Х		Х		Χ		Χ		Χ	Χ		Х	Χ	
Archive: Store at -70°C for 15 years		Х															Xn	

- ^a **Eligible subjects** return 7 days (+/- 1 day) for their first Subgam-VF dose. Infusion visits will be scheduled every 7 days. Individual infusions may be administered at ± 1 day of the planned schedule, if absolutely necessary (e.g. because of unavoidable conflicts, see section 7.2 for details)
- **Week 27** Follow-up visit will occur seven days (+/- 1 day) after the last Subgam-VF infusion. This visit must occur prior to administration of a new IgG product.
- Week 30 Telephone follow-up will occur 28 days (+/- 1 day) after the last Subgam-VF infusion to check for AEs.
- Vital signs will be recorded once during the screening and follow up visits. During Subgam-VF infusion site visits vital signs will be collected 10 minutes before the start of each infusion (+/- 5 minutes) and 30 minutes after stopping the infusion (+/- 15 minutes).
- AEs will be documented from the date of consent until the last follow-up visit. AEs will be collected in subject diaries and by direct observation during each site visit. In addition there will be a telephone follow up by the site on day 3 after each infusion to check for any adverse reactions including infusion site reactions. The date of infusion is considered to be Day 0. If Day 3 is to fall on a weekend or public holiday then this telephone follow up call should be performed on the closest working day after Day 3 as possible.
- Thromboembolic event (TEE) monitoring to be performed at screening and at the follow-up visit- refer to section 7.8 for details
- IgA, IgM testing for IgA and IgM will only occur in those subjects where results are not available for the previous 12 months
- Specific anti-bodies for *Streptococcus pneumoniae* and *Haemophilus influenzae* B will be measured at screening and FU visit. Anti-bodies for measles will be measured at FU visit (this visit must occur prior to administration of a new IgG product as a trough sample is required).
- Virology Serological tests for HBsAg, HCV, HIV 1 & 2 performed at screening and Week 27 FU visit, NAT for HCV and HIV only performed at Week 27 FU visit.
- Parvovirus B19 PCR/NAT and serology
- Direct Coombs' Test and tests for hemolysis will be repeated for the subject at each subsequent clinic visit if the result is positive at any visit
- Haptoglobin, plasma free hemoglobin, urine hemosiderin tests for hemolysis will be repeated for the subject at each subsequent clinic visit if the result is positive at any visit

- PK sampling will begin on Week 21 (prior to 21st infusion of Subgam-VF), with the last sample taken on Week 22 just before the next (22nd) infusion given at the site. Where possible, PK samples and assessments from Steady State Day 1 onwards could be conducted at the subject's home by an appropriately qualified member of the study team, or a Home Health Agency. See Table 3 for PK schedule. If the PK sampling cannot be completed at Week 21 (eg.. due to patients work/vacation schedule) then this can be delayed to start at Week 22, 23, 24 or 25; however, the patient should still visit the office/hospital for their week 21 infusion and complete the other assessments scheduled for Visit 8, if possible. Week 22 assessments (Visit 9) will normally coincide with the PK sampling Day 7. However, if PK sampling is delayed, Visit 9 will also be delayed.
- Archive sample should be collected before an infusion of another product
- **N.B.** The non-shaded columns represent infusions that may be performed at the subject's home. After the Week 2 visit and if an appropriately qualified member of the study team or the subject's care giver is available, then arrangements may be made to conduct some of the visits at the subject's home to reduce the number of visits to the sites. Alternatively a Home Health Agency may be utilized. The subject would be required to sign an extra IRB/EC approved consent form to permit the site to share the subject's details with the agency in order for them to collect the samples/conduct the assessments.

Table 2 Pharmacokinetic Assessment Schedule for Subgam-VF (Week 21 to Week 22a)

	Before start of infusion Day 0	Time after end of infusion							
Evaluation	Approx. -30 min	1 day (24 hours) ± 2 hours	2 days (48 hours) ± 4 hours	3 days (72 hours) ± 6 hours	5 days (120 hours) ± 8 hours	7 days ^b (168 hours) ± 12 hours			
lgG	Х	Х	Х	Х	Х	Х			
Reserve sample	Х	Х	Х	Х	Х	Х			

- a If the PK sampling cannot be completed at Week 21 (eg. due to patients work/vacation schedule) then this can be delayed to start at Week 22, 23, 24 or 25; however, the patient should still visit the office/hospital for their week 21 infusion and complete the other assessments scheduled for Visit 8, if possible. Week 22 assessments (Visit 9) will normally coincide with the PK sampling Day 7. However, if PK sampling is delayed, Visit 9 will also be delayed..
- b The PK sample must be collected before the infusion scheduled for that day is started.
- c In exceptional circumstances, and with prior Sponsor approval, if one of the following PK samples if lost, unevaluable, or not taken it may be taken at the same timepoint during the week following the PK assessment, as long as the same dose in mg/kg has been given:
 - o 1 day (24 hours ± 2 hours)
 - o 2 days (48 hours ± 4 hours)
 - o 3 days (72 hours ± 6 hours)
 - \circ 5 days (120 hours ± 8 hours).

